An exploratory study of the effect of tranexamic acid treatment on the progression of COVID-19
in outpatients

Study Protocol and Statistical Analysis Plan

NCT04338074

Date 05/03/2021

[name], PhD Principal Investigator
University of Alabama at Birmingham
Birmingham, AL 35294

Protocol Summary - in nontechnical, lay language

a. Summarize the purpose and objectives of this protocol in one short paragraph. The current proposal seeks to determine the effect of a 5 day treatment with oral tranexamic acid (TXA) on the outcomes of outpatients who are newly identified (within 72 hours of test result and within 7 days of onset of symptoms) as test positive for the SARS-CoV-2 virus. Subjects receiving COVID-19 testing within the UAB system will be identified and contacted by telephone, informed of the study with its potential risks/benefits. If they agree to proceed, they will be consented, randomized to TXA or placebo treatment. Because of concerns related to hypercoagulability in COVID-19 patients and with TXA treatment, all subjects will also be treated with prophylactic anticoagulation using the anticoagulant, apixaban 5 mg p.o. BID

b. Describe how outcomes will be measured for this protocol. The primary outcome of this study is the need for admission to a hospital due to COVID-19. Secondary outcomes include symptom progression and any other available medical information such as visible bruising.

Background - in nontechnical, lay language

A recent report in Physiological Reviews (attached) proposed that the endogenous protease plasmin acts on SARS-CoV-2 by cleaving a newly inserted furin site in the S protein portion of the virus resulting in increased infectivity and virulence. Patients with hypertension, diabetes, coronary artery disease, cerebrovascular illness, COPD and kidney dysfunction commonly have elevated levels of plasmin/plasminogen and it was proposed that this may be the mechanism for poorer outcomes in patients with these co-morbidities. A logical treatment that might blunt this process would be the inhibition of the conversion of plasminogen to plasmin. Fortunately, there is an inexpensive, commonly used drug, tranexamic acid, TXA, which suppresses this conversion and could be re-purposed for the treatment of COVID-19.

TXA is a synthetic analog of the amino acid lysine which reversibly binds four to five lysine receptor sites on plasminogen. This reduces conversion of plasminogen to plasmin, and is normally used to prevent fibrin degradation. TXA is FDA approved for outpatient use as a treatment of heavy menstrual bleeding (typical dose 1300 mg p.o. TID x 5 days) and off-label use for many other indications. TXA is used perioperatively as a standard-of-care at UAB for orthopedic and cardiac bypass surgeries and so used regularly in the most fragile, elderly patients with multiple co-morbidities where it has been found safe. At UAB, it is commonly employed in hemorrhaging trauma patients and currently is being studied for perioperative use in Cesarean section surgeries. It has also been utilized for spinal surgery, neurosurgery, ENT surgeries, orthognathic surgeries and even long term for the treatment of cosmetic dermatological disorders with a long track record of safety.

Given the potential benefit and limited toxicity of TXA it would appear warranted to perform rapid randomized, double-blind placebo controlled exploratory trials at UAB in the treatment of the early phases of COVID-19 to determine whether it reduces infectivity and virulence of the SARS-CoV-2 virus as hypothesized. Involvement of each patient is only for 7 days before primary endpoints and then intermittent contact until resolution of symptoms out to 30 days.

It is hypothesized that administration of TXA will reduce the incidence of hospitalization of diagnosed COVID-19 outpatients. Potential benefits would be immediate for the patient. Given expected patient numbers in community, 7 days to final assessment and limited "pilot" numbers, it should be rapidly performed.

Participants (Screening and Selection)

a. How many participants are to be enrolled at UAB (if other sites relying on UAB IRB, list the number for each site)? 100

If multi-site study, total number at all sites/institutions: n/a

b. Describe the characteristics of anticipated or planned participants (if multiple groups, repeat list for each group).

Sex: Both sexes

Race/Ethnicity: All

Age: Adults, 19 years of age or older. Younger individuals appear to be at low risk of COVID-19

Health status: COVID-19 positive

c. From what population(s) will the participants be derived? UAB-associated testing sites including the UAB Hospitals, UAB Employee Health, Kirklin Clinic and satellites.

Describe your ability to obtain access to the proposed population that will allow recruitment of the necessary number of participants: A Co-PI of this project, [name], is a faculty of the Infectious Disease Division of the Department of Medicine. She currently is responsible for Employee Health testing and is a member of her divisional task force related to COVID-19 studies at UAB. Identification of patients would be a cooperative effort with the members of the Infectious Disease Division.

d. Describe the inclusion/exclusion criteria:

Inclusion: a recent positive test (within 96 hours of testing; within 7 days of onset of symptoms) for COVID-19; currently an outpatient with no expected immediate hospitalization; English speaking and with phone/internet capability adequate for daily communication. At present, only RNA detecting COVID-19 tests are considered valid and will be the only ones accepted.

Exclusion: an immediate need for hospitalization; history of seizures; history of significant renal disease; history of hypercoagulation-related disorders including pulmonary thromboembolisms, deep venous thromboses, vision/ocular changes; recent or ongoing anticoagulation treatments; cardiac or other vascular stents; active bleeding; history of GI bleed; history of intracranial hemorrhage; pregnancy; use of estrogen-containing oral contraceptives; active malignancy

e. If participants will comprise more than one group or stratification, describe each group (e.g., treatment/intervention, placebo, controls, sham treatment) and provide the number of participants anticipated in each group. Subjects will be randomized into a TXA treatment group (n=50) and a Placebo group (n=50). There will be a post hoc analysis that uses stratification according to high vs. low risk for progression of COVID-19 based on age/comorbidities. Notably, 45% of adult Alabamians qualify for the high risk group: elderly, obesity, hypertension, diabetes, COPD, CAD.

f. Indicate which, if any, of the special populations listed below will be involved in the protocol. Include the Special Populations Review Form (SPRF) if indicated.

Employees or students at institution where research conducted

For each box checked, describe why the group is included and the additional protections provided to protect the rights and welfare of these participants who are vulnerable to coercion: Some of the recruited patients will have been tested through UAB Employee Health. As part of the consent process, they will be informed that involvement or nonparticipation will have no impact upon their jobs and/or academic standing. To exclude this population would be to deprive them of an opportunity to participate.

g. List any persons other than those directly involved in the protocol who will be at risk. If none, enter "None":

None

h. Describe the recruitment process (e.g., medical record review, referrals, letter of invitation, existing patients) that will be used to seek potential participants (e.g., individuals, records, specimens)..

All patients undergoing COVID-19 testing at UAB-associated testing sites (e.g. UAB Hospitals, UAB Employee Health, Kirklin Clinic and satellites) or referred from them to UAB-associated treatment sites (e.g. UAB COVID-19 Clinic) will be given a packet of information (attached) at the time of testing or first contact which they will keep (none returned to study). The packet describes the study, provides contact information for the PI/study personnel. Only patients who contact the study personnel will be recruited.

If a patient has tested positive for COVID-19, they will be informed of the test result by a treating physician.

Working remotely, the study will be described by the PI/study personnel and if the patient agrees to participate in the study, they will be consented using remote methods.

i. Describe the screening process/procedures for potential participants. All newly identified COVID-19 positive patients will be screened for inclusion/exclusion criteria by telephone following informed consent. Demographics, recent/ongoing symptoms and history related to co-morbidities and other health status will be determined.

Protocol Procedures, Methods, and Duration - in nontechnical, lay language

a. Describe the procedures for all aspects of your protocol. Tell us what you are doing.

This study involves the following:

1) Subjects will be randomized into two groups:

(a) tranexamic acid (TXA) 1300 mg by mouth three times per day x 5 days
(b) placebo tablets by mouth three times per day x 5 days.

The clearance half-life of TXA is approximately 3 hours so drug will have washed out by the day following the final treatment.

2) Due to the possible risk of hypercoagulability being greater in the COVID-19 population, all subjects (both TXA and placebo groups) will also be asked to self-administer apixaban (5 mg p.o. BID), in an unblinded fashion as anticoagulation during the 5 day study period.

A minimal exposure “drive-by” interaction will occur in which there is a transfer of treatment materials (drugs and instructions) while the patient remains isolated in their vehicle. This is currently planned for a small component of the off-street parking area immediately adjacent to the 1917 Clinic located at [name]. This interaction will consist of conversation with either one of the investigators or one of the research nurses named in the IRB Personnel Form. As in all physical interactions with COVID-19 patients, study personnel would don appropriate personal protective equipment. Communication will either occur via cell phone or by talking loudly so it can be heard through the window. They will also have 24/7 access to research personnel by phone/internet to ask additional information.

Notably, this “drive-by” interaction has several advantages over the alternative (mailing medications/instructions to patients) in that it assures delivery and initiation of the treatments, it reduces the potential exposure of postal personnel to a known COVID-19 patient.

Contact after the “drive-by” interaction would be exclusively by telephone or via the internet.

All subjects will be contacted by telephone or internet daily and ongoing symptoms will be assessed for 7 days. In subjects with symptoms, additional contact(s) will be made at 3 day intervals for up to 30 days until resolution of any symptoms.

The primary endpoint for the study is hospital admission for COVID-19 within 7 days of enrollment.

b. What is the probable length of time required for the entire protocol (i.e., recruitment through data analysis to study closure)? 6 months

c. What is the total amount of time each participant will be involved? To primary endpoint – daily for 7 days after that, intermittently until resolution of symptoms – for up to a maximum of 30 days.

d. List the procedures, the length of time the procedure takes, the total # of times the procedure is performed, and indicate whether each is performed solely for research or would already be performed for treatment or diagnostic purposes (routine care) for the population.
-Insert additional table rows as needed.
-If procedure is sometimes research and sometimes routine care, include on separate lines with number of times as each.

Procedure	Length of Time Required of Participants	Total # of Times the Procedure is Performed	Research (Res) –OR- Routine Care
Consent	1 hour	1	 Res  Routine
“Drive-by” interaction to pick up study drugs/placebo	30 min	1	 Res  Routine
Daily Phone or email Contact	20-30 min each contact	7 times until primary endpoint, then follow-up at 3 day intervals until symptoms resolve up to 30 days	 Res  Routine

f. Will participants be compensated? Yes No

If Yes, complete i-v.

- i. Type: (e.g., cash, check, gift card, merchandise): Gift card
- ii. Amount or Value: \$50
- iii. Method (e.g., mail, at visit): Received at time of “drive-by” interaction
- iv. Timing of Payments: (e.g., every visit, each month): once
- v. Maximum Amount of Compensation per Participant: \$50

Benefits

Describe the potential benefits of the research.

The participant may benefit directly from participation in this study. Clearly benefits to the patient and society if it is demonstrated that TXA reduces the severity of COVID-19. This pilot study is unlikely to demonstrate definitive results as it is not powered sufficiently for that endpoint (would require 200 patients per group for 50% reduction). It will, however, provide the necessary preliminary data needed for a larger multicenter trial of the same intervention. Its primary purpose is an assessment of safety and the generation of efficacy estimates for TXA.

Risks - in nontechnical, lay language

- a. List the known risks for participants as a result of participation in the research. This should not include the minimal risk of loss of confidentiality. However, it should include any physical, psychological, social,

economic, and/or legal risks. If there is a greater than minimal risk of loss of confidentiality describe why this is so. Do not list risks associated with the standard-of-care procedures.

NOTE: Risks included here should be included in the consent form or information sheet, as applicable.

The drug tranexamic acid (TXA) is commonly employed at UAB as its administration is a standard-of-care in association with orthopedic and cardiac bypass surgeries. There is an extensive clinical literature associated with its use and it is FDA-approved for the treatment of heavy menstrual bleeding using the same dose as is utilized in the present study. It is available Over-The-Counter in the UK. That said, it is not without risks as its primary indication is as an inhibitor of plasmin activation. Plasmin is a protease that breaks down the fibrin in clots and so there is an increased risk of clot formation when TXA is utilized. For that reason, use is typically excluded in people with a history of forming clots such as in Deep Venous Thrombosis (DVT) or Pulmonary Thromboembolus (PTE). Patients will be instructed that if they demonstrate signs/symptoms of DVT or PTE (i.e. swollen limbs, distended veins, sudden onset of shortness of breath) at the time of enrollment or during the study (they are asked these questions during the regular telephone contacts), they are to immediately inform the research nurse and will be instructed to go to an Emergency Room for evaluation/treatment. They will also immediately stop any study medications. There has also been reports of seizures in individuals who receive high doses of TXA intravenously. Although these are not expected, patients will be instructed to let family members know that they should call the research nurses and/or immediately go to an Emergency Room if there is any alteration in mental status or uncontrolled muscle contractions.

Because there are concerns that TXA as well as COVID-19 might increase risks of forming blood clots, subjects will all be treated with a an oral anticoagulant, apixaban at a dose demonstrated to be effective prophylaxis in clinical conditions commonly treated at UAB (5 mg p.o. BID). All blood thinners have risks, in particular risks of increased bleeding and subjects will be excluded if they have a medical history suggesting increased risk from anticoagulants (e.g. history of GI bleed).

b. Estimate the frequency, severity, and reversibility of each risk listed.

SIDE EFFECTS REPORTED IN THE FDA APPROVAL STUDIES FOR TXA

Table 2: Adverse Events Reported by ≥ 5% of Subjects Treated with TXA	3900 mg/day n (%) (N=232)	Placebo n (%) (N=139)
Total Number of Adverse Events	1500	923
Number of Subjects with at Least One Adverse Event	208 (89.7%)	122 (87.8%)
HEADACHE^a	117 (50.4%)	65 (46.8%)
NASAL & SINUS SYMPTOMS^b	59 (25.4%)	24 (17.3%)
BACK PAIN	48 (20.7%)	21 (15.1%)
ABDOMINAL PAIN^c	46 (19.8%)	25 (18.0%)
MUSCULOSKELETAL PAIN^d	26 (11.2%)	4 (2.9%)
ARTHRALGIA^e	16 (6.9%)	7 (5.0%)
MUSCLE CRAMPS & SPASMS	15 (6.5%)	8 (5.8%)
MIGRAINE	14 (6.0%)	8 (5.8%)
ANEMIA	13 (5.6%)	5 (3.6%)
FATIGUE	12 (5.2%)	6 (4.3%)

^aIncludes headache and tension headache

^b Nasal and sinus symptoms include nasal, respiratory tract and sinus congestion, sinusitis, acute sinusitis, sinus headache, allergic sinusitis and sinus pain, and multiple allergies and seasonal allergies

^c Abdominal pain includes abdominal tenderness and discomfort

^d Musculoskeletal pain includes musculoskeletal discomfort and myalgia

^e Arthralgia includes joint stiffness and swelling

The following adverse reactions have been identified from post-marketing experience with TXA.

Because these reactions are reported voluntarily from a population of uncertain size, it is not always possible to reliably estimate their frequency or establish a causal relationship to drug exposure.

Based on worldwide post-marketing reports, the following have been reported in patients receiving TXA for various indications:

- Nausea, vomiting, and diarrhea
- Allergic skin reactions
- Anaphylactic shock and anaphylactoid reactions
- Thromboembolic events (e.g., deep vein thrombosis, pulmonary embolism, cerebral thrombosis, acute renal cortical necrosis, and central retinal artery and vein obstruction)
- Impaired color vision and other visual disturbances
- Dizziness

Risks of TXA & seizures reported in cardiac surgeries – at doses of 24-50 mg/kg IV (versus the bioequivalent dose of <10 mg/kg given in this study) the incidence was 1.4%. No seizures were reported in the FDA studies of oral dosing. There are three case reports of seizures in non-cardiac cases all using IV administration of TXA.

RISKS OF APIXABAN. Hemorrhagic clinical events reported to be related to long-term (>6 mo) apixaban therapy occurred at an incidence of approximately 1.5%. Non-hemorrhagic clinical events were <1%. Use of a 5 day course would have less risk and the effects of apixaban can be readily and immediately reversed.

Informed Consent

a. How will consent be obtained?

Patients interested in participating will be emailed a copy of the consent form. The PI/study personnel will verbally present the study by going over the consent form. The PI/study personnel will arrange a video (Zoom) conference with the subject and a witness (who may be someone already in the subject's household). The call will include the following: (1) Identification of who is on the call, (2) Review of the consent form by the PI/study personnel and answering any questions the subject may have, (3) Confirmation by the witness that the subject's questions have been answered, (4) Confirmation by the PI/study personnel that the subject is willing to participate in the study and sign the consent form while the witness is listening on the phone, (5) Verbal confirmation by the subject that they would like to participate in the study and that they have signed and dated the consent form.

The signed consent form then be scanned/photographed and emailed back to the PI/study personnel. A copy of the consent form signed by the investigator and witness will be placed in the study record. Following FDA guidelines, a hard copy of the consent form signed by the subject will not be retained (e.g., due to potential contamination of the document by infectious material).

Statistical Plan

Update (5/2/2021) The statistical plan for this study was to compare categorical data for the primary endpoint which was hospital admission during the 7 day treatment period. A simple Chi Square comparison was planned. Any secondary data were to be described qualitatively and not analyzed statistically.

In this truncated study, no subjects met the primary endpoint and there were insufficient data to perform any meaningful analysis.

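### Under the primary endpoint as written, a participant who dies before hospital admission has no event and falls in the favourable cell; death is not named as an outcome anywhere

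*Combined protocol and SAP*

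**What the plan says.** The endpoint is described in three places.

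- Protocol Summary, item b: "The primary outcome of this study is the need for admission to a hospital due to COVID-19".
- Protocol Procedures, Methods, and Duration, item a: "The primary endpoint for the study is hospital admission for COVID-19 within 7 days of enrollment".
- Statistical Plan: the plan was to "compare categorical data for the primary endpoint which was hospital admission during the 7 day treatment period", and "A simple Chi Square comparison was planned".

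On other outcomes, Protocol Summary item b says "Secondary outcomes include symptom progression and any other available medical information such as visible bruising", and the Statistical Plan adds "Any secondary data were to be described qualitatively and not analyzed statistically".

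Three further statements bear on the point. Risks, item a, says that "there is an increased risk of clot formation when TXA is utilized". Protocol Procedures, item a, says "Contact after the “drive-by” interaction would be exclusively by telephone or via the internet". The Benefits section gives safety assessment and the estimation of efficacy, ahead of a larger multicenter trial, as the main purpose.

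**The concern.** Death without admission prevents the primary event from ever occurring. A two-category comparison with no place for death therefore ranks the worst possible outcome with recovery at home. Participants are outpatients who are not seen in person after collecting their drugs, so a death before admission is possible. If it came from a clot related to TXA, it would fall in the TXA arm, add nothing to that arm's admission count, and leave TXA looking better than it is. A trial meant to assess safety and supply efficacy estimates for a larger trial should not have a primary measure that can work in that direction, and the larger trial could inherit the definition.

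**Working it through.** **1. The three endpoint descriptions side by side**

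| Place | Event | Window | Death |
|---|---|---|---|
| Protocol Summary, item b | Need for admission due to COVID-19 | None given | Not mentioned |
| Protocol Procedures, item a | Admission for COVID-19 | 7 days from enrollment | Not mentioned |
| Statistical Plan | Hospital admission, cause not specified | 7-day period | Not mentioned |

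Under the second and third, a participant who dies unadmitted has no admission and belongs in the non-event cell. An analyst who set that participant to missing would lose the death instead. Neither handling counts it as a failure. The Protocol Summary description might reach a COVID-19 death at home, but no adjudication rule says so.

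**2. The plan's own figure**

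The Benefits section says 200 patients per group would be needed for a 50% reduction. Control rate, alpha, sidedness and power are not given, so the figure cannot be reproduced from the documents alone. Assuming 20% v 10%, two-sided alpha 0.05 and 80% power, with the pooled-variance formula:

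n = [1.96 × √(2 × 0.15 × 0.85) + 0.842 × √(0.20 × 0.80 + 0.10 × 0.90)]² / 0.10² = (0.990 + 0.421)² / 0.01 ≈ 199 per group.

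The figure is consistent with that assumption, though other control rates fit under other settings. It is not shown to be wrong, and serves here only as an assumed base.

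**3. Effect of one unadmitted TXA death at the planned 50 per arm (assumed counts)**

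Risk ratio = (a/50) / (b/50) = a/b.

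| Admissions, TXA v placebo | RR, admission only | With one TXA death added | RR, admission or death | Share of apparent reduction lost |
|---|---|---|---|---|
| 3 v 5 | 0.60 | 4 v 5 | 0.80 | (0.40 − 0.20)/0.40 = one half |
| 5 v 10 | 0.50 | 6 v 10 | 0.60 | (0.50 − 0.40)/0.50 = one fifth |

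The second row matches the assumed 20% v 10%. Its uncorrected chi-square p-value goes from 0.16 to 0.28.

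Approximate 95% intervals for the first row use SE(log RR) = √(1/a − 1/50 + 1/b − 1/50):

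- 3 v 5: SE 0.702, interval 0.15 to 2.4.
- 4 v 5: SE 0.640, interval 0.23 to 2.8.

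**4. Chance of at least one such death among 100 participants**

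1 − (1 − d)^100 gives 9.5%, 39% and 63% at assumed rates d of 0.1%, 0.5% and 1%.

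**5. Equal and unequal deaths in a trial of the larger size**

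Endpoint of admission or death, on the 20% v 10% base, with d the assumed rate of death without admission:

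| d | Equal in both arms: n per group (power at 200) | TXA arm only: n per group (power at 200) |
|---|---|---|
| 0.1% | 201 (80.0%) | 204 (79.3%) |
| 0.5% | 205 (79.1%) | 224 (75.4%) |
| 1% | 210 (78.1%) | 253 (70.2%) |
| 2% | 221 (76.1%) | 329 (58.8%) |

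Equal rare deaths barely matter. The definition matters when deaths are unequal.

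**The case against.** The strongest reply is that the documents contain no rule scoring death as non-admission or as success. That is right: the placement follows from the definition, and the looser summary wording could be read to cover a COVID-19 death at home. What stands is that nothing makes that reading operative, and the text closest to the analysis does not support it.

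A reader might also infer more than the documents say about risk. The 45% high-risk figure in Participants, item e, describes adult Alabamians, not expected enrollees, and the exclusions in item d remove several groups with serious illness or clot history. For COVID-19 the protocol names hypercoagulability and blood clots; pulmonary thromboembolism is discussed in connection with TXA.

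There are real mitigations. Contact is daily for 7 days, staff can be reached at all hours, clot symptoms are asked about with direction to an Emergency Room, and both arms receive an anticoagulant. These make an unadmitted death less likely, and a fatal clot would also bear on the safety objective. They do not settle how such a death enters the primary comparison.

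On size, a reader might take the loss of half the apparent benefit as the expected distortion. It comes from one choice of counts; at 5 v 10 the loss is one fifth. Both shifts lie within the sampling error of a 100-patient pilot that the protocol itself calls underpowered. One TXA death in 50 with none on placebo is a 2% v 0% split that nothing in the documents supports.

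**Conclusion.** The point holds as a weakness of the endpoint definition. Death before admission has no place in the primary comparison, and the literal reading puts it in the favourable cell. The possible bias runs towards TXA if unadmitted deaths are more frequent in that arm, which the acknowledged clot risk makes a fair design concern.

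Its size is unknown. Every count and rate of unadmitted death used above is assumed, and the 20% v 10% base is an assumption that merely fits the stated 200 per group.

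A reader might infer that this trial's result was distorted. The documents do not support that: the Statistical Plan reports a truncated study with no primary events and no meaningful analysis. Equally, because death is outside the endpoint, that statement does not tell the reader whether anyone died.

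**What to change.** Define the primary endpoint as hospital admission for COVID-19 or death from any cause within 7 days of enrollment. Use that definition in Protocol Summary item b, Protocol Procedures item a and the Statistical Plan, whose three descriptions now differ. Show admissions and deaths separately by arm, so that a composite result cannot hide which component drives it.

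The cost is a one-sentence definition carried into three places. The downside is that deaths unrelated to COVID-19 or study drug would count; these should be rare over 7 days.

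The change does not cover everything. A non-fatal clot admission judged not to be for COVID-19 would still be a non-event, so clot admissions need to be visible in the safety reporting. The plan should also say how participants lost to remote contact are classified, since a death at home could go unseen that way.

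For the truncated study, state the number of deaths by arm, including if it is zero. Carry the composite definition into the larger trial.

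### The primary endpoint is limited to COVID-19 admissions in two sections and unrestricted in the Statistical Plan, with no rule for assigning cause, so a TXA-related clot admission could go uncounted

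*Combined protocol and SAP*

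**What the plan says.** The combined protocol and SAP describes the primary endpoint in four places.

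- Protocol Summary, item b: "The primary outcome of this study is the need for admission to a hospital due to COVID-19". Restricted by cause, with no time window in that sentence.
- Protocol Procedures, Methods, and Duration, item a: "The primary endpoint for the study is hospital admission for COVID-19 within 7 days of enrollment". Restricted by cause, with a window.
- Background, on the hypothesis: "It is hypothesized that administration of TXA will reduce the incidence of hospitalization of diagnosed COVID-19 outpatients". No cause stated.
- Statistical Plan: "primary endpoint which was hospital admission during the 7 day treatment period". No cause stated. The seven days are called the treatment period, although study drug is given for five.

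On clotting, Risks, item a says that "there is an increased risk of clot formation when TXA is utilized". It explains the use of apixaban in everyone with the words "Because there are concerns that TXA as well as COVID-19 might increase risks of forming blood clots". It lists the signs of a clot that should send a participant to an Emergency Room: "swollen limbs, distended veins, sudden onset of shortness of breath".

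The Statistical Plan tests only the primary endpoint, by chi-square; everything else is described without a test. The Benefits section gives safety, together with efficacy estimates for a larger trial, as the main purpose. No section defines a COVID-19 admission, names who decides the cause, or provides for adjudication.

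**The concern.** Whether an admission counts depends on which section is followed and, under the restricted wording, on an attribution for which there is no rule. The attribution is hardest for the harm that the protocol expects from TXA. Sudden breathlessness in an infected participant may be disease progression, a clot related to the disease, or a clot related to the drug.

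If clot admissions are classed as not being for COVID-19, any true excess caused by TXA drops out of the TXA arm's count. The remaining comparison flatters TXA. The excluded events are then only described, in a study whose stated purpose includes safety and whose estimates are meant to feed a larger trial.

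**Working it through.** **1. The plan's own figure.** The Benefits section says 200 per group would be needed for a 50% reduction. It gives no control rate, alpha, sidedness or power. Assume 20% v 10%, two-sided alpha 0.05, 80% power, and no continuity correction:

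n = [1.960·√(2·0.15·0.85) + 0.842·√(0.20·0.80 + 0.10·0.90)]² / (0.10)² = (0.990 + 0.421)² / 0.01 ≈ 199.

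The figure is therefore plausible with a control rate near 20%. It does not decide this point; it only gives a scale for step 5.

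**2. What counts under each wording.**

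| Admission within 7 days | Protocol Summary and procedures section | Statistical Plan |
|---|---|---|
| COVID-19 respiratory worsening | counts | counts |
| Clot, cause uncertain | undefined | counts |
| Clot attributed to study drug | does not count | counts |
| Bleed | does not count unless attributed to COVID-19 | counts |

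**3. Why blinding does not remove the problem.** Suppose staff who do not know the arm class every clot admission as not for COVID-19. If k such admissions per arm come from the disease and d more come from TXA, the rule removes k from placebo and k + d from TXA. The same rule, applied evenly, takes d more events from the TXA arm.

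**4. Size at 50 per arm.** All counts and rates here are assumptions; the documents give none.

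- Admissions of 5/50 placebo and 5/50 TXA give a risk ratio of 1.0. Leaving out two TXA clot admissions gives 3/50 v 5/50, a risk ratio of 0.06/0.10 = 0.6. The chi-square is 0.04² / (0.08·0.92·2/50) = 0.54, p = 0.46.
- At admission rates of 5% to 20%, the expected count per arm is 2.5 to 10. One admission is 1/2.5 = 40% to 1/10 = 10% of that count.
- Near the significance boundary, 10 v 3 gives chi-square 0.14² / (0.13·0.87·2/50) = 4.33, p = 0.037. Counting one more TXA clot admission, 10 v 4, gives 0.12² / (0.14·0.86·2/50) = 2.99, p = 0.084. Neither uses a continuity correction. Fisher's exact test gives 0.071 and 0.148, so the crossing depends on the test variant.

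**5. Effect on a follow-on trial.** Assume 20% control admission, COVID-19 admissions halved to 10%, and x further clot admissions per 100 on TXA. The all-cause risk ratio is (10 + x)/20. Sample sizes use the formula in step 1.

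| x per 100 | All-cause risk ratio | n per arm | Power at 200 per arm |
|---|---|---|---|
| 0 | 0.50 | 199 | 80% |
| 1 | 0.55 | 253 | 70% |
| 2 | 0.60 | 329 | 59% |
| 4 | 0.70 | 615 | 36% |

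A cause-restricted endpoint that left these clots out would show 0.50 in every row. With x = 2, control rates of 10% and 30% give all-cause risk ratios of 0.70 and 0.57.

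**The case against.** The strongest reply is that the Statistical Plan already states an unrestricted endpoint, under which clot and bleed admissions count. That stands: a reader might infer that the trial counts COVID-19 admissions only, and the documents do not settle this. They conflict.

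Second, COVID-19 admission is a legitimate endpoint for a pilot asking whether TXA slows the disease. In the 5 v 5 example a reader might see a 40% reduction where none exists. That goes too far: if two TXA admissions really were drug-related clots, 5 v 3 is the right count of COVID-19 admissions. What it hides is the lack of any net difference in admissions.

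Third, exclusion of clots is possible, not documented. The protocol itself links hypercoagulability to COVID-19, so a clot might be counted, and TXA v placebo is double-blind. This stands, so attribution is undefined rather than impossible. A reader might also conclude that both TXA and the disease are said to cause clots; the text states a raised risk for TXA and only a concern for COVID-19.

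Fourth, a reader might extend the argument to bleeding. The protocol does warn that "All blood thinners have risks, in particular risks of increased bleeding", but apixaban goes to both arms and bleeding is not tied to COVID-19. The documents give no ground for a between-arm bias from bleeds.

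Finally, clot symptoms are asked about at the regular telephone contacts, so such events would be described. They would not be tested.

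**Conclusion.** The point holds in limited form. Two sections restrict the endpoint by cause, two do not, and none says how cause is assigned. Under the restricted wording, a true excess of TXA clot admissions could leave the primary count and every statistical comparison, and the error would favour TXA. In an arm of 50, each such admission is worth 10-40% of the expected count at assumed admission rates of 5-20%. The size of any real bias is unknown, because the documents give neither an admission rate nor a clot rate for this population.

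The Statistical Plan reports a truncated study in which nobody met the primary endpoint, so no reported comparison is shown to change. It does not say whether any admission was set aside because of its cause. The practical weight is in clarifying that and in the larger trial for which this pilot was meant to supply estimates.

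**What to change.** Reconcile the Protocol Summary, the procedures section and the Statistical Plan to one endpoint: hospital admission for any cause within 7 days of enrollment. This fits the Statistical Plan's unrestricted wording and the hypothesis. Record the reason for each admission (respiratory/COVID-19, thromboembolic, bleeding, other) before unblinding, and list it by arm.

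If the COVID-19 restriction is kept, write down how cause is assigned, and compare all-cause admission by arm beside it with the same test.

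The cost is an edit to the wording and one reason-for-admission field. A rare unrelated admission in seven days adds a little noise, and study staff must assign the reason while blinded. The change affects only how events are counted, not clinical management.
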